STUDY SUMMARY

STUDY OVERVIEW	
Full title	Renal function Assessment with Point of Care creatinine In Diverse populations (RAPID)
Objectives	
Study A
 
 • To compare capillary POC-Cr with venous serum enzymatic creatinine concentrations (serum Cr) in people of different ethnicities performed by health care professionals and patients • To compare estimated glomerular filtration rate (eGFR) using POC-Cr and serum Cr with formal GFR assessment in people of different ethnicities • To define a threshold of POC-Cr concentration in different ethnicities which are confirmatory of eGFR <60mls/min/1.73m² (Kidney Disease Improving Global Outcomes; KDIGO Definition Stage 3) and a range of POC-Cr which may require further confirmation 
Study B
 
 • To conduct an observational cohort study of serial capillary self-testing POC-Cr for at least one week. • To compare single and serial capillary POC-Cr compared with single venous creatinine concentration IDMS traceable enzymatic assay • To assess test success rate, safety, training time, patient experience and acceptability of serial capillary POC-Cr testing
Type of trial	Two centre cross-sectional study and prospective longitudinal cohort study
Trial design and methods	
375 participants (including > 40 of African/African-Caribbean ancestry) having venous serum creatinine and 99mTc-DTPA nuclear medicine or venous GFR filtration panel testing will be recruited to a cross sectional study (Study A)
 
At least 40 patients with CKD will be recruited to a longitudinal study (Study B)
 
Demographics, medical and transportation details will be recorded
 
Finger-prick capillary creatinine will be assessed by POC-Cr device; Venous serum creatinine concentration (Isotope Dilution Mass Spectrometry (IDMS) Traceable Enzymatic assay).
 
Participants will be trained to use POC-Cr device, asked to self-monitor up to four times per day and report details including test failure and adverse events.
 
Patient experience and acceptability will be assessed using Service User Technology Acceptability Questionnaire.

Health condition(s) or problem(s) studied	Chronic Kidney Disease
Target sample size	At least patients 415 (Study A: 375; Study B: At least 40)
Trial duration per participant:	Study A: 1 Day Study B: 1 week

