
Main inclusion/exclusion criteria:
	
Inclusion criteria:
 
 • Is 18 years of age or older • Is willing to complete all study procedures • Study A: Patients undergoing formal nuclear medicine (99mTc-DTPA) glomerular filtration rate testing or willing to have a venous GFR filtration panel (Study A only) • Study B: Has Chronic Kidney disease (CKD) KDIGO criteria or is at risk of CKD due to heart disease or diabetes as determined by physician 
Exclusion criteria:
 
 • Unable or unwilling to give informed consent • Any condition which would make finger prick contraindicated e.g. severe skin conditions, bleeding disorder • Study A: If formal GFR testing has been requested only because estimated GFR is not considered to reflect true GFR (e.g. liver disease)

Statistical methodology and analysis:
	
 • Accuracy compared to venous serum creatinine and 99mTc-DTPA testing or GFR filtration panel will be calculated for POC-Cr capillary blood testing performed by patients and health care professionals. • Total, between-day, and within-day precision will be evaluated by comparing up to four POC-Cr capillary concentrations for at least seven days and compared to day 1 and 8 venous serum creatinine concentrations.

STUDY TIMELINES
	

Study Duration/length
	
End date 30/06/2025

Expected Start Date
	
1/7/20

End of Study definition and anticipated date
	
Last patient completed final study visit

Key Study milestones
	
 • Month 1-28: Recruitment • Month 29: Data analysis • Month 30 Outcome presentation/publication

STORAGE of SAMPLES (if applicable)
	

Human tissue samples
	
N/A

Data collected / Storage
	
Pseudoanonymised data will be stored for 5 years after study completion in secure filing cabinets in the renal research team locked room.

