Recently, use of ethnicity in kidney function testing has been recommended to be removed. New biomarker GFR filtration panels which do not require adjustment for ethnicity have been

demonstrated to provide better estimation of measured GFR and can be performed without the need for costly nuclear medicine assays⁹. In addition, assessment of lean body weight may enhance estimation equations¹⁰ but have not been assessed in combination with POC-Cr testing.

In other chronic diseases, self-monitoring is associated with feelings of security, reassurance, control, high motivation and levels of satisfaction¹¹ and has transformed care for millions of individuals (e.g. glucose testing). Self-monitoring with POC-Cr testing could empower kidney patients to participate in their own care, enable timely intervention at times of deterioration, and reduce unnecessary hospital visits and damage to veins. Home POC-Cr testing has been demonstrated in a small paediatric study to be an acceptable alternative to hospital testing¹².

Self-monitoring with POC-Cr was strongly supported by AAF engagement participants if appropriate self-care material and education is provided and proposed benefits included privacy of personal monitoring or in a faith-based community setting at the individual's convenience. This approach was considered ideal for those identified to have early CKD at screening event with minimal health care professional contact. However, in order to harness the benefits of POC-Cr self-monitoring it will be important to understand and interpret intra-patient variability in capillary blood results, potentially without need for complete alignment with laboratory tests. Conversely, self-monitoring may introduce increased anxiety and requirement for additional interaction with health care services and concurrent understanding of feasibility (training required, number of successful tests) and patient experience (including acceptability of monitoring frequency) of self-monitoring POC-Cr is critical.

Our overall aim is to develop and pilot a UK community-based screening and CKD monitoring program to address health inequalities in CKD, focusing on people from ethnic minority groups.

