Study A: POC-Cr will be assessed using the NovaMaxCreat and Epoc devices. Finger-prick capillary whole blood samples will be taken (0.05 uL for NovaMaxCreat and 0.9 uL for Epoc) using lancets by the research team. Venous serum creatinine for routine care (Isotope Dilution Mass Spectrometry (IDMS) Traceable Enzymatic assay) and ^{99m}Tc-DTPA glomerular filtration rate testing (where available) will be extracted from hospital laboratory databases. Participants not undergoing routine ^{99m}Tc-DTPA glomerular filtration rate testing will also have a 'eGFR filtration panel assessment – Beta-2-microglobulin, cystatin-C (processed by Synlab/ViaPath) and beta-trace-protein concentration (processed by Affinity laboratories), assessment on their venous blood sample.

Participants will be trained to use the POC-Cr device by the research team and time taken recorded and asked to perform one POC-Cr test.

In addition, the Epop Blood Analysis system, will also measure capillary potassium concentrations, which will be compared to serum potassium (taken from the venous blood sample for routine clinical care). This will be tested in the laboratory using the Roche Chemistry Analyser Cobas 8000.

Study B: Participants will be trained to use the POC-Cr device, NovaMaxCreat (NovaBio) by the research team and time taken recorded. Participants will be taught how to perform quality controls. All sample results will be digitally recorded by the device and downloaded after the device is returned. Participants will be asked to do one test at the hospital (with a simultaneous lab creatinine on site for validation), then to self-monitor four times per day (first thing in morning, midday, before evening meal/early evening, before bed) and each test recorded in a paper diary or electronically as desired. Details reported will include date and time of test, test success, device and non-device failures (test results, missed testing and reasons for missed test (e.g. forgot, did not want to test) and adverse events (e.g. pain or infection or prolonged injury after sampling, pre-syncopal or syncopal episode).

For participants who perform finger-prick testing for capillary blood glucose monitoring, both samples (creatinine using NovaMaxCreat and glucose using their usual device) can be taken from the same finger-prick test. However, participants will be advised to take the creatinine sample first.

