Accuracy of self-monitoring for the first and last reading taken by the participant will be assessed as outlined in Study A. Total, between-day, and within-day precision will be evaluated by comparing up to four POC-Cr capillary concentrations for seven days and compared to day 1 and 8 venous serum creatinine concentrations. Mean and standard deviation for each time point during the week, and within the day will be compared by an independent means *t*-test and *F*-test, respectively, using Stata Version 21 or greater. A *p*-value of less than 0.05 will be considered significant.

SUTAQ scale scores, relationships between scales and group differences on scales will be reported and compared with demographics, frequency, success and accuracy of testing.

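### Study B compares time points with independent-samples t- and F-tests although the same participants supply every time point; the tests ignore pairing and do not estimate the promised precision components

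*Protocol*

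**What the plan says.** Section 3 of the Protocol asks Study B participants to do one test at the hospital and "then to self-monitor four times per day (first thing in morning, midday, before evening meal/early evening, before bed"). Table 2 in section 4 adds patient tests at the Day 1 and final visits. Recruitment is stated as "At least 40 patients with CKD will be recruited to a longitudinal study (Study B").

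The Study Summary and section 8 both promise precision components. Section 8 reads: "Total, between-day, and within-day precision will be evaluated by comparing up to four POC-Cr capillary concentrations for seven days", set against the Day 1 and Day 8 venous values. It names no estimator for them. The only method it names for the serial readings is: "Mean and standard deviation for each time point during the week, and within the day will be compared by an independent means" t-test, and an F-test respectively, where a p-"value of less than 0.05 will be considered significant". The first and last self-tests are also assessed for accuracy by the Study A agreement methods.

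Section 1 explains why the serial readings matter: "it will be important to understand and interpret intra-patient variability in capillary blood results".

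**The concern.** Every time point, whether a day of the week or a slot in the day, holds readings from the same people. Independent-samples tests are built for different people in each group.

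- **The t-test** judges a mean difference against the full spread of creatinine between participants, although that spread cancels when each person is compared with themselves.
- **The F-test** compares SDs taken across participants. Section 3 recruits purposively over a range of renal disease severity, so those SDs should be mostly differences between people. A change in repeatability within a person is diluted.

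The error runs towards non-significance. What is at stake is the interpretation of the serial data: time points could show no significant difference while within-person shifts or a loss of repeatability go unseen. The named tests also do not produce the total, between-day and within-day components that the plan promises.

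**Working it through.** The protocol gives no power, SD or sample-size derivation for Study B, so there is no figure to reproduce. The check shows how the named tests behave under stated assumptions.

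**Inputs from the Protocol.** n = 40 participants (Study Summary); four tests a day for seven days, so 4 × 7 = 28 scheduled home readings each (section 3; more are allowed); significance level 0.05 (section 8; two-sided assumed). The benchmark shift is 8.87%, the allowable total error for creatinine in section 8. It is stated there for analytical error against a reference, and is used here only as a yardstick.

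**Assumptions.** Between-person CV b = 20%, 30% or 50%; within-person CV w = 8%, doubled to 16% to represent lost precision. Two groupings, since the protocol does not fix one: one reading per person per time point (N = 40 per group), and seven per person pooled over the week (N = 280 per group).

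**Step 1: share of variance that is between people.** b² / (b² + w²). For b = 30%: 0.0900 / 0.0964 = 93%. For 20% it is 86%; for 50%, 97.5%.

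**Step 2: type I error of the t-test.** The test assumes the mean difference has variance 2(b² + w²)/N, but the person effect cancels and the true variance is 2w²/N. Under no shift the t statistic therefore has SD of about √(w² / (b² + w²)). For b = 30% that is √(0.0064 / 0.0964) = 0.26 rather than 1, so the critical value of about 1.99 lies 7.7 SDs out. Simulation (4,000 runs per scenario) gave 0 to 0.1% for the independent t- and F-tests, against 4.4 to 5.5% for within-person tests.

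**Step 3: observed shift needed for significance.** t_crit × √(2(b² + w²)/N).

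| Grouping | b | Shift needed | Detects 8.87%: independent t | Detects 8.87%: paired t |
|---|---|---|---|---|
| N = 40 | 20% | 1.99 × √(2 × 0.0464/40) = 9.6% | 37% | 99.9% |
| N = 40 | 30% | 1.99 × √(2 × 0.0964/40) = 13.8% | 1.5% | 99.7% |
| N = 40 | 50% | 1.99 × √(2 × 0.2564/40) = 22.5% | 0% | 99.8% |
| N = 280 | 20% | 1.96 × √(2 × 0.0464/280) = 3.6% | 100% | 100% |
| N = 280 | 30% | 1.96 × √(2 × 0.0964/280) = 5.1% | 100% | 100% |
| N = 280 | 50% | 1.96 × √(2 × 0.2564/280) = 8.4% | 71% | 100% |

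The detection rates are simulated.

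**Step 4: F-test when within-person CV doubles.** Expected variance ratio = (b² + 0.16²) / (b² + 0.08²). The two-sided 5% critical value is 1.89 for N = 40 and 1.27 for N = 280.

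| b | Expected ratio | Independent F, N = 40 | Pitman-Morgan, N = 40 | Independent F, N = 280 | Within-person F, N = 280 |
|---|---|---|---|---|---|
| 20% | 0.0656 / 0.0464 = 1.41 | 10% | 34% | 90% | 100% |
| 30% | 0.1156 / 0.0964 = 1.20 | 0.7% | 18% | 27% | 100% |
| 50% | 0.2756 / 0.2564 = 1.07 | 0% | 10% | 0.2% | 100% |

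A true ratio of 4 in within-person variance (0.16² / 0.08²) appears as 1.07 to 1.41, depending only on case mix.

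**Step 5: sensitivity.** With lognormal creatinine, a day-to-day CV of 5% and readings pooled over the week, the independent t-test finds a 5% shift about 35% of the time at a between-person log-SD of 0.3 and about 0.1% at 0.5. For an 8.87% shift the rates are about 100% and 47 to 56%. The pattern is the same.

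**The case against.** The strongest reply is that the tests are not blind. Pooled over the week, the independent t-test finds an 8.87% shift 71 to 100% of the time, and at a between-person CV of 20% the F-test finds a doubled within-person CV 90% of the time. That stands. A reader might infer that these tests can never detect anything, or that the F ratio stays near 1 whatever happens to precision; the calculations do not support either.

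A reader might also infer that the protocol will take non-significance as proof of adequate precision. It says no such thing. It promises precision components separately, and it checks the first and last self-tests by agreement methods. Nor is precision a listed objective: section 2 names serial self-testing, comparison with venous creatinine, success rate, safety, training time, patient experience and acceptability. Precision is an analysis aim in the Study Summary and section 8. A charge that time-of-day effects go unexamined would fail too, since section 8 compares means within the day.

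Finally, an SAP may supply the estimator for the precision components. That answers their omission here, but not the named tests: an SAP that follows section 8 would inherit them.

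**Conclusion.** Wrong as written. Section 8 names independent-samples tests for readings that sections 3 and 4 show are repeated on the same people. That conclusion needs no assumption.

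The size does rest on assumptions, because the protocol gives no spreads and does not fix how readings are grouped. Under those used here, type I error is near 0% in every scenario. Loss of power ranges from negligible (pooled t-test, 8.87% shift, between-person CV of 20% or 30%) to nearly total (one reading per person, CV of 30% or more; or the pooled F-test at 50%). In no scenario do the tests estimate total, between-day or within-day precision.

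The supportable consequence is a risk: a non-significant result may be uninformative about intra-patient variability. The error is conservative, loses no data, and leaves Study A and the first-and-last-reading accuracy analysis untouched.

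**What to change.** Replace the t-test and F-test sentence in section 8 with a nested random-effects (variance-components) model on log POC-Cr:

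- random terms for participant, day within participant, and residual;
- fixed effects for day and time of day;
- within-day, between-day and total within-person CV, each with a 95% confidence interval, as the reported results;
- time-point differences tested as within-person contrasts in the same model.

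Split the residual into device and biological variation only if numeric quality-control values are in fact recorded. Section 3 describes daily quality control to confirm that the reagent batch conforms, but does not say the values are kept for analysis.

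The cost is one paragraph of wording and slightly more complex modelling. The core change needs no new data.

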9 PATIENT AND PUBLIC INVOLVEMENT (PPI)

We hosted an engagement event with Africa Advocacy Foundation (London Research Design Service funded) for sixteen African/Afro Caribbean participants who strongly welcomed future opportunities to have CKD screening in their local community and self-monitoring. Key recommendations that have contributed to this proposal and for future work include:

- BAME champions from PPI events will be used to explain study details if required
- Studies should NOT be African ancestry specific as perception of 'victimisation' – 'high risk' group recruitment preferred.
- Concern about home surveillance due to 'spying' – would need adequate reassurance about data safety/ownership
- A focussed dissemination event not desired but text/WhatsApp message and email to website link to findings with preferred presentation format in video/ infographics

In addition, King's Kidney Care PPIE Group including patients with CKD have contributed to this proposal. They were highly supportive of the proposal and considered the potential for POC kidney function testing to be 'transformative' due to it being 'accessible, cost-effective, reliable,

rapid and simple' and that 'real time feedback' through a future App development would increase patient confidence. They welcomed the opportunity to enable patients to participate more actively in their care, and recommended that up to four times daily testing would be acceptable to patients for one week (in keeping with diabetes testing). King's Kidney Care PPIE Group and Africa Advocacy Engagement participants will help with review of study patient material, data interpretation and dissemination.

10 FUNDING AND SUPPLY OF EQUIPMENT

The study funding has been reviewed by the KCH R&I Office and deemed sufficient to cover the requirements of the study. The research costs for the study have been supported by British Renal Society.

11 DATA HANDLING AND MANAGEMENT

All paper data recording sheets will be stored in lockable filing cabinets at the renal research team office for 5 years. Electronic data spreadsheets will be kept on the private renal research team T drive and will be password protected. Patients details, will be replaced by a study ID number before data is transferred in to a contracted general data protection regulation (GDPR) compliant storage provider, named Redcap (Research Electronic Data Capture). This will be removed after 5 years.

All staff involved in this research project will ensure data is handled with strict confidentiality in line with local trust policies. Data will be reviewed regularly by the research team.

12 MATERIAL/SAMPLE STORAGE

No samples will be stored from the study.

13 PEER AND REGULATORY REVIEW

The study has been peer reviewed in accordance with the requirements outlined by KCH R&I.

The study was deemed to require regulatory approval from the following bodies (list). Each approval will be obtained before the study commences.

- HRA
- REC

14 ADVERSE EVENTS AND INCIDENT REPORTING

14.1 Definitions of Adverse Events

Term	Definition
Adverse Event (AE)	Any untoward medical occurrence in a patient or study participant, which does not necessarily have a causal relationship with the intervention/treatment/procedure involved.
Serious Adverse Event (SAE).	Any adverse event that: 
 • results in death, • is life-threatening*, • requires hospitalisation or prolongation of existing hospitalisation**, • results in persistent or significant disability or incapacity, or • consists of a congenital anomaly or birth defect

*A life- threatening event, this refers to an event in which the participant was at risk of death at the time of the event; it does not refer to an event which hypothetically might have caused death if it were more severe.
 
** Hospitalisation is defined as an in-patient admission, regardless of length of stay. Hospitalisation for pre-existing conditions, including elective procedures do not constitute an SAE.
	

14.2 Assessments of Adverse Events

Each adverse event will be assessed for severity, causality, seriousness and expectedness as described below.

Severity

Category	Definition
Mild	The adverse event does not interfere with the participant's daily routine, and does not require further procedure; it causes slight discomfort
Moderate	The adverse event interferes with some aspects of the participant's routine, or requires further procedure, but is not damaging to health; it causes moderate discomfort
Severe	The adverse event results in alteration, discomfort or disability which is clearly damaging to health

Causality

The assessment of relationship of adverse events to the procedure is a clinical decision based on all available information at the time of the completion of the case report form.

The following categories will be used to define the causality of the adverse event:

Category	Definition
Definitely:	There is clear evidence to suggest a causal relationship, and other possible contributing factors can be ruled out.
Probably:	There is evidence to suggest a causal relationship, and the influence of other factors is unlikely
Possibly	There is some evidence to suggest a causal relationship (e.g. the event occurred within a reasonable time after administration of the study procedure). However, the influence of other factors may have contributed to the event (e.g. the participant's clinical condition, other concomitant events).
Unlikely	There is little evidence to suggest there is a causal relationship (e.g. the event did not occur within a reasonable time after administration of the study procedure). There is another reasonable explanation for the event (e.g. the participant's clinical condition).
Not related	There is no evidence of any causal relationship.
Not Assessable	Unable to assess on information available.

Expectedness

Category	Definition
Expected	An adverse event which is consistent with the available information about the intervention/treatment/procedure in use in this study.
Unexpected	An adverse event which is not consistent with the available information about the intervention/treatment/procedure in use in this study*

* this includes listed events that are more frequently reported or more severe than previously reported

